### 10.3 Statistical Analyses

Descriptive statistics will include: number of subjects and frequencies in % for categorical variables and mean and standard deviation for continuous variables. Kaplan-Meier estimates will be calculated for survival outcomes and where appropriate for adverse event outcomes.

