cause death or disabling stroke at 2 years (Hazard Ratio: 0.89; 95% Confidence Interval (CI): 0.73 to 1.09;  $p=0.25$ ). All-cause mortality occurred in 16.7% of those randomized to TAVR with SAPIEN XT, compared with 18.0% of those treated with SAVR. Disabling stroke occurred in 6.2% of patients treated with TAVR and 6.3% of patients treated with SAVR (18). In a propensity score-matched comparison of the SAPIEN 3 TAVR patients and PARTNER II Cohort A SAVR patients, TAVR demonstrator noninferiority and superiority to SAVR (propensity score pooled weighted proportion difference: -9.2%; 95% CI: -13.0 to -5.4;  $p<0.0001$ ). At 1 year, the rate of all-cause death was 7.4%, disabling stroke occurred in 2%, reintervention was required in 1%, and moderate or severe paravalvular leak (PVL) was seen in 2% (19).

As a result of these and other findings, the American College of Cardiology (ACC)/American Heart Association (AHA) guideline committees have provided TAVR with a Class I and IIa recommendation for patients with severe AS with high/prohibitive and intermediate surgical risk, respectively (20). And according to the 2017 European Society of Cardiology (ESC)/ European Association for Cardio-Thoracic Surgery (EACTS) guidelines on valvular heart diseases, TAVR is favored over SAVR in elderly patients with suitable transfemoral access and elevated surgical risk (21).

This study will evaluate the SAPIEN 3 Ultra System. The SAPIEN 3 Ultra THV design differs from the SAPIEN 3 design only with respect to the weave of the outer skirt and attachment of the skirt to the frame. The SAPIEN 3 Ultra Delivery System allows the THV to be crimped directly onto the deployment balloon eliminating the need for valve alignment and reducing the number of procedural steps.

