## 3 STUDY DESIGN

This is a prospective, single-arm, multicenter study. Up to 110 subjects will undergo the procedure at up to 8 participating centers. Subject follow-up will occur at 30 days, 6 months and annually through five years.

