### 8.3 AE Reporting Requirements

All AEs will be captured from the time of enrollment until subject participation has ended (i.e. completion of study or discontinuation). See section 8.3.1 for events that are not required to be reported to Edwards.

Pre-existing medical conditions or symptoms reported prior to subject enrollment will not be recorded as an AE. In the event there is a worsening in the pre-existing medical condition or symptoms due to the device or study-related procedure, then an AE must be recorded.

Death should not be recorded as an AE, but should be reflected as an outcome to another specific AE.

If known, the diagnosis for an AE should be recorded, rather than listing individual signs and symptoms.

All AEs will be reported in subject medical records, and the appropriate eCRF throughout the duration of the study, and will be followed until resolution, stabilization or study completion.

All SAEs and Device Deficiencies that might have led to a SAE should be reported to Edwards immediately, but not later than 3 calendar days after site study personnel's awareness of the event.

Other AEs must be reported to Edwards as soon as practical but no later than 10 working days of awareness.

Information must be entered into the electronic database or, when the electronic database is not available, reported directly to the Edwards Safety Officer. In the event that the EDC system is not in service, a paper copy of the AE CRF must be e-mailed to [contact] according to the timelines described above.

At the time of initial AE notification, the following minimal information must be provided:

- Subject ID
- AE term/diagnosis
- AE onset date

For selected events, the site might be requested to provide to Edwards (or designee) a copy of

anonymized supporting documentation (such as hospital record, laboratory results, autopsy results).

All AEs will be reviewed by the Edwards Safety Officer. Each AE will be assessed as to its relationship to the study device and/or implant procedure, whether it was anticipated or not anticipated, and whether it qualifies as an SAE and USADE.

Depending on the local requirements or following agreement between both parties, Edwards or the Principal Investigator will be responsible for performing safety reporting to the EC according to the relevant local regulatory requirements.

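### Section 10.3 names Kaplan-Meier as the only time-to-event method for adverse events and gives no rule for deaths; cumulative incidence with death as a competing event would be better for late non-fatal events

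*Combined protocol and SAP*

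**What the plan says.** Section 10.3 names two kinds of summary that could apply to adverse events. The first is descriptive: "number of subjects and frequencies in % for categorical variables". The second is time-to-event: "Kaplan-Meier estimates will be calculated for survival outcomes and where appropriate for adverse event outcomes". It does not list the adverse events that will get a curve, say what makes a curve appropriate, or say how a death enters the analysis of a non-fatal event.

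The period is long. Section 3 states: "Subject follow-up will occur at 30 days, 6 months and annually through five years". Section 8.3 states: "All AEs will be captured from the time of enrollment until subject participation has ended". Section 8.3 also says how deaths are recorded: "Death should not be recorded as an AE, but should be reflected as an outcome to another specific AE". That is a data-entry convention and does not tell the analyst whether a death censors or competes.

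The primary endpoint (Section 5.1) is assessed on leaving the procedure room. Both secondary endpoints (Section 5.2) run only to discharge.

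**The concern.** For a non-fatal event, a subject who dies first can no longer have it. If that death is treated as censoring, Kaplan-Meier assumes that the dead subject's later risk equals that of the subjects still under observation. One minus Kaplan-Meier then estimates the risk in a setting where nobody dies. A reader will usually take it as the share of treated subjects who have the event, and for that purpose it is too high. The gap widens with follow-up time and with mortality.

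Appendix B defines several events that can occur late: reintervention, structural valve deterioration, endocarditis, valve thrombosis and repeat hospitalization. Section 9.1 says that long-term results with these valves are not yet known. At stake is the accuracy of any late non-fatal event rate reported from this cohort.

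**Working it through.** The plan gives no adverse event rate and no five-year mortality for intermediate-risk patients, so it has no figure of its own to reproduce here. The size has to be built from the mortality in Section 1.2 plus stated assumptions.

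**Inputs**
- SAPIEN 3, intermediate risk: 7.4% all-cause death at one year (Section 1.2).
- SAPIEN XT, intermediate risk: "All-cause mortality occurred in 16.7% of those randomized to TAVR with SAPIEN XT" (Section 1.2). This is read as a two-year figure, because the sentence before it gives a two-year endpoint.
- Assumed, not in the documents: constant death hazard d, constant event hazard e, and a five-year Kaplan-Meier event rate of 5% or 10%.

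**Step 1: death hazards**
- d = -ln(1 - 0.074) = 0.0769 per year; five-year mortality 1 - exp(-5 × 0.0769) = 31.9%.
- d = -ln(1 - 0.167)/2 = 0.0914 per year; five-year mortality 36.7%.

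**Step 2: the two estimands at time t**
- Kaplan-Meier, deaths censored: 1 - exp(-e·t).
- Cumulative incidence: e/(e + d) × (1 - exp(-(e + d)·t)).

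**Step 3: five years, even accrual**

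For a Kaplan-Meier rate of 5%, e = -ln(0.95)/5 = 0.01026. With d = 0.0769: 0.01026/0.08714 × (1 - exp(-0.4357)) = 4.16%. With d = 0.0914: 0.01026/0.10162 × (1 - exp(-0.5081)) = 4.02%.

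| Kaplan-Meier rate | Mortality source | Cumulative incidence | Excess, points | Excess, relative |
|---|---|---|---|---|
| 5% | 7.4% at 1 year | 4.16% | 0.8 | 20% |
| 5% | 16.7% at 2 years | 4.02% | 1.0 | 24% |
| 10% | 7.4% at 1 year | 8.3% | 1.7 | 20% |
| 10% | 16.7% at 2 years | 8.1% | 1.9 | 24% |

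**Step 4: earlier reporting times, even accrual, Kaplan-Meier rate of 5% at five years**

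Relative excess: 0.3-0.4% at 30 days, about 2% at 6 months, 4-5% at 1 year, 8-9% at 2 years and 11-14% at 3 years. Check at one year: Kaplan-Meier is 1.021% against 0.982% or 0.975%, ratios 1.039 and 1.046.

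**Step 5: uneven event timing, read at five years**

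Let H be the total five-year event hazard. A share s falls evenly in the first 30 days and the rest evenly afterwards, with the Step 2 formula applied piecewise.
- s = 50%: excess 9-11%.
- s = 75%: about 5%.
- s = 90%: about 2%.
- All events between the end of year 3 and year 5: cumulative incidence = exp(-3d) × b/(b + d) × (1 - exp(-2(b + d))) with b = H/2; excess 36-44%.

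**Step 6: other five-year mortality, even accrual, Kaplan-Meier rate of 5%**

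Mortality of 20%, 25%, 30%, 40% or 50% gives an excess of about 11%, 15%, 19%, 27% or 38%.

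**Step 7: scale against sampling error**

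With 110 treated subjects, the standard error of a 5% rate is √(0.05 × 0.95/110) = 2.1 points, against an excess of 0.8-1.0 points.

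**The case against.** Five points can be made for the plan as it stands.

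First, Kaplan-Meier is not the only method named. Section 10.3 also provides counts and percentages, and its proviso leaves the use of Kaplan-Meier for adverse events open. With complete follow-up, a crude percentage does estimate the cumulative incidence: a simulation under the second mortality input gave 4.04% against the exact 4.02%. This stands, and it limits the point to the time-to-event analyses. It does not settle the matter, because follow-up will not be complete. Section 7.9 lets subjects leave early when no valve was implanted or the valve was explanted, and anticipates other discontinuations. With such exits a crude percentage tends to be too low and Kaplan-Meier too high. Aalen-Johansen handles both deaths and exits.

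Second, the text does not itself say that deaths will be censored. That is true; it is the usual practice, and the plan gives no other rule.

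Third, mortality may be lower here than in the cited cohorts. Section 6.2 excludes life expectancy under 24 months and significant frailty, and the 16.7% belongs to a different valve. This stands as a reason for a range.

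Fourth, the excess is smaller than the sampling error. That is correct for rates of 5-10% at this sample size. But the excess is systematic, its direction is known, and it does not shrink with more subjects or with pooling.

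Fifth, a reader might infer that five-year adverse event rates are the study's main long-term product. The documents do not say so. Section 2 sets a procedural objective, and no five-year adverse event rate is a named endpoint.

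**Conclusion.** The point holds as an inexpensive improvement. Section 10.3 leaves the handling of deaths open and names no time-to-event method suited to non-fatal events over five years. If deaths are censored, the five-year excess is about 20-24% in relative terms. That figure rests on three assumptions: cited one- or two-year mortality extrapolated to five years, a constant death hazard and a constant event hazard.

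A reader might infer that every adverse event rate will be overstated by a fifth to a quarter. The documents do not support that. Depending on timing and horizon, the excess runs from almost nothing (periprocedural events, early reports) to above 35% (events confined to the last two years). A five-year mortality of only 20% would bring the even-accrual figure down to about 11%.

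Nor does the point touch the study's conclusion on procedural success. The primary and secondary endpoints end at procedure-room exit and at discharge, where competing mortality has essentially no room to act.

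**What to change.** In Section 10.3, replace the sentence on Kaplan-Meier with text to this effect: *Kaplan-Meier estimates will be given for all-cause death. For non-fatal adverse events reported at time points beyond 30 days, cumulative incidence from Day 0 will be estimated by the Aalen-Johansen method, with death before the event as a competing event and subjects who leave the study alive censored at exit. Kaplan-Meier figures for these events will be given as a supplement.*

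Starting the clock at Day 0 (Section 7.6) makes clear that early events count and that this is not a landmark analysis of late-onset events. It also helps to state that an event which proves fatal counts as the event at its onset, in keeping with the recording rule in Section 8.3. For reports at 30 days or earlier the choice of method makes almost no difference.

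The change needs no new data and leaves the sample size and endpoints as they are; the estimator is standard. There are two costs. The main figures become slightly less comparable with earlier Kaplan-Meier-based reports, which the supplement meets. The text also changes by written amendment under Section 12.6, with the ethics and regulatory steps that apply, so it is best bundled with another amendment.

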## 11 STUDY ADMINISTRATION

### 11.1 General Study Organization

Edwards is the Study Sponsor and has the overall responsibility for the conduct of the study, including assurance that the study meets the regulatory requirements.

Edwards will be responsible for obtaining appropriate approvals prior to study commencement, selecting investigators, ensuring that sites have IRB/EC approval prior to device shipment, and conducting clinical site monitoring to ensure that subjects are being properly consented and the study is being conducted according to the protocol. Edwards will notify investigative sites of enrollment closure.

Edwards will maintain copies of correspondence, data, shipment of devices, adverse device effects and other records related to the clinical study as appropriate.

### 11.2 Case Review Board

The Case Review Board is comprised of physicians experienced with Edwards THV products for treatment of AS in the intermediate risk population. The role of the Case Review Board is to review submitted cases to determine if the subject is an appropriate candidate for the study, with

a focus on confirming subject operative risk, valve sizing, appropriate vascular access, valve morphology and any relevant clinical factors impacting enrollment eligibility.

### **11.3 Echocardiographic Core Lab**

An independent echocardiographic core lab will review and analyze echocardiographic images. A standardized protocol for acquiring images and training will be provided to the clinical sites prior to study initiation.

### **11.4 Image Management**

An image transfer vendor will receive, maintain and provide cardiac images (echocardiogram and CT) to the appropriate personnel for analysis.

Instructions for image upload will be provided to study site personnel prior to study initiation. Study site personnel should make every reasonable effort to upload all images to the image transfer vendor within 5 business days of image acquisition. Any unscheduled imaging performed related to the safety or performance of the device should also be uploaded.

### **11.5 Histopathology**

Histopathology will be performed on all explanted valves. Explants will be prepared, preserved and shipped to the Histopathology Core Lab per instructions provided by Edwards.

### **11.6 Study Site Selection**

Site and investigator selection criteria will be established to ensure that the study personnel and their institutions are qualified to screen, perform and manage the study procedures as well as support the associated requirements for research.

### **11.7 Site Personnel Training**

Training by Edwards or its designee is required for study site personnel in accordance with the roles outlined in the DoA log. Training will include review of the device IFU, study protocol, case review process, identification of eligible subjects, instructions on data collection, standardized image acquisition, methods for soliciting data from alternative sources and regulatory requirements.

Training may be provided in one of the following formats: in-person training sessions, teleconference, online via WebEx/Skype, or read and review. Retraining may be performed for sites who have demonstrated protocol or implant procedure compliance issues.

Documentation of study site personnel qualifications and training will be maintained in the site's study files with copies sent to Edwards.

## **11.8 Device Management**

### **11.8.1 Investigational Device**

All investigational devices will be supplied by Edwards. Unique identifiers associated with any device should be recorded in the subject's medical file as well as on the implant card that is given to the subject.

### **11.8.2 Device Storage**

All investigational device components provided for the study should be stored in a secure location where only study personnel can access the device for use.

### **11.8.3 Device Accountability**

The study site will maintain detailed records of the receipt and disposition of all investigational devices. Device disposition will be verified by the monitor periodically throughout the study. The Investigator will return unused devices to Edwards along with the completed device accountability log at completion of enrollment. Use of the investigational devices and accessories provided for use in this study is prohibited outside of this protocol.

## **11.9 Data Management**

This study will use a secure, password protected EDC system accessible via the Internet. A unique Subject ID will be assigned for each subject enrolled in the study. All pertinent data will be entered by the study site and core lab personnel into eCRFs.

Every reasonable effort should be made to complete data entry within 5 business days of data collection. Data review by Edwards personnel will occur remotely as well as during on-site monitoring. Data discrepancies will be queried and resolved through the EDC system.

The site Principal Investigator or designee must ensure the accuracy and completeness of the recorded data and provide his/her electronic signature on the appropriate eCRFs at regular intervals during the study, as requested by Edwards. If changes are made to data previously signed-off, a new electronic signature will be required to acknowledge/approve the changes.

## **11.10 Monitoring Procedures**

All study sites will be monitored periodically by Edwards or designee to ensure compliance with the protocol and the Investigator's Agreement and that all study subjects have been properly consented. The monitor will ensure that the completed eCRFs match the medical records and work with the site to resolve differences through electronically-generated queries or formal action items.

### **11.11 Site Discontinuation**

Edwards has the right to discontinue an Investigator or study site for the following reasons:

- Failure of the Investigator to enroll subjects into the study at an acceptable rate
- Failure of the Investigator to comply with pertinent regulations of appropriate regulatory authorities
- Insufficient adherence to protocol requirements
- Submission of knowingly false information from the research facility to Edwards, the monitor, or any regulatory authority.

If a study site is discontinued, subjects enrolled prior to discontinuation will continue to be followed per the protocol.

### **11.12 Auditing**

The study may be subject to a quality assurance audit by Edwards or a designee, as well as inspection by appropriate regulatory authorities. It is important that the Investigator and relevant study site personnel are available during any audits and that sufficient time is devoted to the process. In the event of an audit by regulatory authorities, the Investigator should contact Edwards as soon as possible.

### **11.13 Publication Policy**

Publication or presentation of the overall clinical study results and/or site-specific results requires prior written approval of Edwards. If Edwards approves the publication or presentation of the overall clinical study results and/or site-specific results, then Institutions and Investigators will comply with the Publications and Public Disclosure Section of the Clinical Trial Agreement. Edwards will provide statistical support for the publication process.

The study results will be made public within 24 months of the end of data collection and a full report of the outcomes will be made public no later than three (3) years after the end of data collection.

## **12 ETHICAL AND REGULATORY CONSIDERATIONS**

### **12.1 Applicable Principles and Regulations**

The study will be performed in accordance with the ethical principles that have their origin in the Declaration of Helsinki (as updated in Fortaleza Brazil in 2013).

The following regulations and guidelines will be followed:

- ISO 14155: 2011 Clinical Investigation of Medical Devices for Human Subjects - Good Clinical Practice
- MDD 93/42/EEC European Medical Device Directive 93/42/EEC (MDD)

- MEDDEV 2.7/3 revision 3 Clinical Investigations: Serious Adverse Event Reporting under Directives 90/385/EEC AND 93/42/EEC
- MEDDEV 2.12-1 revision 8: Guidelines on a Medical Device Vigilance System
- General Data Protection Regulation 2016/679
- Specific country regulations will be fulfilled, as applicable

## **12.2 Institutional Review Board/Ethics Committee**

This protocol, the proposed ICF, other written subject information and any proposed advertising material must be submitted to the IRB/EC for written approval. A copy of the written IRB/EC approval of the protocol and ICF must be received by Edwards before recruitment of subjects into the study and shipment of investigational product.

The Investigator must submit and, where necessary, obtain approval from the IRB/EC for all subsequent protocol amendments and changes to the ICF.

The Investigator is responsible for obtaining annual IRB/EC approval and renewal throughout the duration of the study. Copies of the Investigator's reports and the IRB/EC continuance of approval must be sent to Edwards.

## **12.3 Informed Consent**

Edwards will provide a sample ICF to the Investigator to prepare for use at his/her site. The site-specific ICF, and any subsequent modifications, must be in agreement with current regulations and guidelines and must be approved by Edwards prior to submission to the IRB/EC. The reviewing IRB/EC must approve the ICF before use at the site.

Before participating in the clinical study, each subject must give written Informed Consent after the context of the study has been fully explained in a language that is easily understood by the subject. The subject must also be given the opportunity to ask questions and have those questions answered to his/her satisfaction.

A copy of each subject's signed and dated consent form must be maintained by each Investigator in a designated clinical study administrative file. A signed copy of the consent form must be given to each subject. The consent process must be documented in the subject's medical chart; the documentation should include minimally that consent was obtained prior to participation in the research study, date consent was obtained, and confirmation that a copy of the consent was given to the subject.

## **12.4 Confidentiality**

All data used in the analysis and reporting of this evaluation will be without identifiable reference to the subject. Authorized personnel assigned by Edwards will have access to the confidential files and will have the right to inspect and copy all records pertinent to this study.

